9.2.3 Medical History

Part A and Part B

Medical history will be coded using the Medical Dictionary for Regulatory Activities (MedDRA). For the FAS, medical history will be summarized descriptively by system organ class (SOC) and preferred term (PT). The corresponding data listing will also be provided.

In addition, the number of subjects reported to have had positive cultures for respiratory pathogens within the 2 years prior to screening (i.e., answered yes on the respiratory microbiology form) will be summarized for the FAS. The corresponding data listing will be provided.

9.2.4 Prior and Concomitant Medications

Part A and Part B

Medications will be coded using the World Health Organization Drug Dictionary (WHODD) and categorized as follows:

- **Prior medication:** any medication that administered during the 56 days before the first dose of study drug in the corresponding Part.
- **Concomitant medication:** medication continued or newly received during the corresponding TE period.
- **Post-treatment medication:** medication continued or newly received after the corresponding TE period.

A given medication may be classified as follows: prior, concomitant, post-treatment, both prior and concomitant, both concomitant and post-treatment, or prior, concomitant, and post-treatment.

If a medication has a completely missing or partially missing start date or stop date and it cannot be determined whether it was taken before the first dose date, concomitantly, or after the TE period, it will be classified as prior, concomitant, and post-treatment. Details for imputing missing or partial start and/or stop dates of medication are described in [Appendix B](#).

Concomitant medications will be summarized descriptively for the FAS using frequency tables by: 1) preferred name (PN); and 2) anatomic class (ATC) level 1, ATC level 2, and PN. For Part B, prior medications will also be summarized the same way as concomitant medications. All medications will be listed for each subject.

9.2.5 Study Drug Exposure

Part A and Part B

Study drug exposure summaries will be based on the Safety Set.

Duration of study drug exposure (in days) will be calculated as: last dose date – first dose date + 1 day, regardless of study drug interruption.

Study drug exposure (in days for Part A; in weeks for Part B) will be summarized descriptively by the number of subjects (n), mean, SD, median, min, and max. It will also be summarized using counts and percentages for Treatment Period categories. For Part A, categories are specified as: ≤ 2 days; >2 and ≤ 4 days; >4 and ≤ 8 days; >8 and ≤ 15 days; >15 days. For Part B, they are specified as: ≤ 15 days; >15 days and ≤ 4 weeks; >4 and ≤ 8 weeks; >8 and ≤ 12 weeks; >12 and ≤ 16 weeks; >16 and ≤ 20 weeks;

>20 and ≤ 24 weeks; >24 weeks. Additionally, the total study drug exposure, defined as the sum total of the study drug exposure across all subjects (in patient-weeks for Part A; in patient-weeks and patient-years for Part B), will be provided.

9.2.6 Study Drug Compliance

Part A and Part B

Study drug compliance will be summarized based on the FAS.

Study drug compliance will be calculated as: $100 \times [1 - (\text{total number of days of study drug interruption}) / (\text{duration of study drug exposure in days})]$. A study drug interruption on a given day is defined as an interruption of any study drug dose or component on that day. In addition, for Part B, a study drug interruption that continues through the end of the study participation (i.e., subject does not resume study drug before the end of the study participation) will not be included in the compliance calculation.

Study drug compliance will be summarized descriptively by the number of subjects (n), mean, SD, median, min, and max. It will also be summarized in categories: <80% and $\geq 80\%$ using frequency tables.

In addition, percentage of tablets taken will be calculated using the following formula: $100 \times [(\text{total number of tablets dispensed}) - (\text{total number of tablets returned})] / (\text{total number of tablets planned to be taken per day} \times \text{duration of study drug exposure in days})$. A summary similar to that for study drug compliance will be produced based on the FAS.

9.2.7 Important Protocol Deviations

Part A and Part B

An important protocol deviation (IPD) is a deviation that may significantly affect the completeness, accuracy, or reliability of the study data or that may significantly affect a subject's rights, safety, or well-being. IPD rules will be developed and finalized before the data lock for Part A.

Protocol deviations that should be considered as potential IPDs include, but are not limited to:

- Subject was enrolled in the study despite not satisfying one or more inclusion/exclusion criterion
- Subject was less than 80% compliant with study drug for non-safety reasons
- Subject received prohibited concomitant medications
- Subject received the wrong treatment or incorrect doses

The occurrence of any of these events should be considered as a potential IPD, but the team should categorize such an event as an IPD only if it has the potential to affect the completeness, accuracy, or reliability of the study data or the subject's rights, safety, or well-being.

For Part A, IPDs will only be provided in an individual subject data listing. For Part B, besides the listing, a summary table of IPDs based on the FAS will also be provided.

9.3 Efficacy Analysis

9.3.1 Efficacy Summary for Part A

Only summary tables based on the FAS will be provided for efficacy assessments in Part A.

9.3.1.1 Spirometry

For spirometry measurements, a summary of raw values, absolute and relative change from baseline values will be provided at each scheduled time point for the following parameters: FEV₁ (L), forced vital capacity (FVC) (L), FEV₁/FVC (ratio), forced expiratory flow (FEF_{25%-75%}) (L/s), ppFEV₁, percent predicted FVC, percent predicted FEF, and percent predicted FEV₁/FVC. The predicted values from spirometry will be calculated using the Global Lung Initiative (GLI) equation. Details on GLI equation are described in [Appendix C](#).

9.3.1.2 Sweat Chloride

The raw values and change from baseline values of sweat chloride measurements will be summarized descriptively (n, mean, SD, median, min, and max) at baseline and post-baseline visits.

9.3.1.3 Weight, Height, BMI and their Z-scores

The raw values and change from baseline values of weight, height, BMI and their z-scores will be summarized descriptively (n, mean, SD, median, min, and max) at baseline and post-baseline visits.

9.3.2 Efficacy Analysis for Part B

There is no multiplicity adjustment; *P*-values provided for the secondary and other endpoints in Part B are considered nominal.

All efficacy analyses described in this section will be based on the FAS, unless otherwise specified. The analysis will include all available measurements through the last scheduled visit, including measurements after treatment discontinuation.

9.3.2.1 Analysis of Primary Efficacy Variables

Not applicable.

9.3.2.2 Analysis of Secondary Efficacy Variables

9.3.2.2.1 Definition of Variables

Percent predicted FEV₁ (ppFEV₁): the ppFEV₁ value is the ratio of FEV₁ (L) and predicted FEV₁ (L), expressed as a percentage. See [Appendix C](#) for more details.

Sweat chloride (SwCl): the SwCl value for a given visit will be calculated as the mean of the non-missing sweat chloride measurements obtained on the left and right arms at that visit. If one of the two arm measurements at a time point is missing, the other will be used as the mean. A volume ≥ 15 μ L is required for an accurate determination of sweat chloride. Any results reported as having volume < 15 μ L will be considered missing for analysis purposes. Any sweat chloride values reported as < 10 mmol/L or > 160 mmol/L will be considered missing for analysis purposes.

Cystic Fibrosis Questionnaire-Revised (CFQ-R): the CFQ-R^{1,4,6} is a validated CF-specific instrument that measures quality-of-life domains. This study utilizes two different versions of CFQ-R:

- CFQ-R for Children ages 6 to 11

- CFQ-R for Parents/Caregivers

In both versions, specific questions belonging to a domain is scored 1, 2, 3, or 4. The CFQ-R domain score, e.g., physical domain score or respiratory domain score, is defined as a scaled score as follows:

$$\text{Scaled score for a domain} = 100 \times (\text{mean (scores of all questions in the domain)} - 1) / 3,$$

where the score from a negatively phrased question is first reversed, i.e., reversed score = 5 – actual score, so that 1 always represents the worst condition and 4 the best condition. The (scaled) domain score ranges from 0 (worst condition) to 100 (best condition). The scaled score for a specific domain will not be calculated if more than half of the questions in the domain have missing scores.

Body mass index (BMI): the BMI at each visit is calculated using the weight and height at each visit as follows:

$$\text{BMI} = \text{Weight (kg)} / [\text{Height (m)}]^2$$

BMI z-score: the BMI score, adjusted for age and sex, will be referred to as BMI-for-age z-score (BMI z-score). The BMI z-score will be calculated by using Centers for Disease Control and Prevention (CDC) growth charts⁸, with the age (in months) used for the calculation defined in [Appendix A](#).

Height z-score and Weight z-score: the height z-score and weight z-score, adjusted for age and sex, will be referred to as weight-for-age z-score (weight z-score) and height-for-age z-score (height z-score). The weight z-score and height z-score will be calculated by using Centers for Disease Control and Prevention (CDC) growth charts⁸, with the age (in months) used for the calculation defined in [Appendix A](#).

Modified Facial Hedonic Scale: refer to Section 11.3.1 of the CSP for details.

Pulmonary exacerbation (PEX): A PEX is defined as a new or changed antibiotic therapy (intravenous [IV], inhaled, or oral) for any 4 or more of the following signs/symptoms:

- Change in sputum
- New or increased hemoptysis
- Increased cough
- Increased dyspnea
- Malaise, fatigue, or lethargy
- Temperature above 38°C (equivalent to approximately 100.4°F)
- Anorexia or weight loss
- Sinus pain or tenderness
- Change in sinus discharge
- Change in physical examination (PE) of the chest
- Decrease in pulmonary function by 10%
- Radiographic changes indicative of pulmonary infection

The **PEX analysis period** will include the time from the first dose date of study drug until the last efficacy assessment, which may be collected up to the Week 24 Visit or the earlier of Day 169 and the end of study participation if the subject does not have the Week 24 Visit.

The number of PEX through Week 24 is then defined as the total number of PEX during the PEX analysis period.

Lung clearance index (LCI): the LCI assessments are derived from N₂-multiple-breath washout (MBW) testing. Each MBW will be performed in multiple replicates for each visit and the final LCI value will be calculated from the technically acceptable washout replicates as graded and determined by a central reader. The following algorithm is used to derive the LCI values at each visit based on the multiple replicates:

- When there is only one acceptable replicate at the visit, the LCI values will not be calculated. The assessment for that subject at the corresponding visit will be missing.
- When there are 2 or more acceptable replicates at the visit, the mean of the values for the acceptable replicates will be calculated as the LCI value at the corresponding visit.

9.3.2.2.2 Analysis Method

Absolute change in ppFEV₁ from baseline through Week 24:

Absolute change from baseline in ppFEV₁ will be analyzed using a mixed-effects model for repeated measures (MMRM) approach based on the FAS. The MMRM will be used to estimate the within-group mean absolute change in ppFEV₁ through Week 24. The model will include absolute change from baseline in ppFEV₁ (including all measurements up to Week 24 [inclusive], both on-treatment measurements and measurements after treatment discontinuation) as the dependent variable, and visit as the fixed effect, with baseline ppFEV₁ value and genotype group (F/F vs. F/MF) as covariates. The model will be estimated using restricted maximum likelihood. Denominator degrees of freedom for the *F*-test of fixed effects will be estimated using the Kenward-Roger approximation². An unstructured covariance structure will be used to model the within-subject errors. If the model estimation does not converge, a compound symmetry covariance structure will be used instead. Conditional on the observed data and covariates, missing data will be assumed to be missing at random; consequently, no imputation of missing data will be performed.

The results obtained from the model will be the average treatment effect through Week 24. Note that the Day 15 Visit will not be included in the estimation of the average treatment effect through Week 24 as the treatment effect is not expected to reach the steady state at Day 15. The estimated mean change from baseline in ppFEV₁ through Week 24, along with the corresponding 2-sided 95% confidence interval (CI) and *P*-value will be provided. The treatment effect at each post-baseline visit with 95% CI, obtained from the model, will be provided as well.

The analysis will be conducted with the clinic spirometry data only. An additional analysis may also be performed to include pooled spirometry data obtained in clinic and by Air Next Spirometer, if the Air Next Spirometry data are assessed to be reasonably consistent with clinic spirometry data.

Absolute change in sweat chloride from baseline through Week 24:

Analysis of this PD variable will be based on an MMRM similar to the analysis of the absolute change in ppFEV₁ from baseline through Week 24 with the baseline sweat chloride included as a covariate instead of baseline ppFEV₁. Data obtained from Day 15, Week 4, Week 12, and Week 24 Visits will be included in the model. However, Day 15 Visit will not be included in the estimation of the average treatment effect through Week 24 as the treatment effect is not expected to reach the steady state at Day 15.

Absolute change in the CFQ-R respiratory domain score from baseline through Week 24:

Analysis of this domain (child's version) will be based on an MMRM similar to the analysis of the absolute change in ppFEV₁ from baseline through Week 24 with the baseline CFQ-R respiratory domain score (child's version) included as a covariate instead of baseline ppFEV₁. Data obtained from Week 4, Week 8, Week 12, Week 16, and Week 24 Visits will be included in the model and all of these visits will be included in the estimation of the average treatment effect through Week 24. The analysis will include only the clinic assessed CFQ-R RD score. An additional analysis may be performed to include CFQ-R RD score assessed at clinic and at home, if the home assessed data are consistent with the clinic assessed data.

Absolute change in BMI and BMI-for-age z-score from baseline at Week 24;

Absolute change in weight and weight-for-age z-score from baseline at Week 24;

Absolute change in height and height-for-age z-score from baseline at Week 24:

Analysis of these variables will be based on an MMRM similar to the analysis of the absolute change in ppFEV₁ from baseline through Week 24 with the corresponding baseline included as a covariate instead of baseline ppFEV₁. Data obtained from Day 15, Week 4, Week 8, Week 12, Week 16, and Week 24 Visits will be included in the model.

Drug acceptability assessment using Modified Facial Hedonic Scale:

Analysis of this variable will be based on descriptive statistics. The number and percentage (based on the FAS) of subjects in each category will be summarized for each question at all scheduled visit. The analysis will include only the data assessed at clinic. An additional analysis may be performed to include the data assessed at clinic and at home, if the home assessed data are consistent with the clinic assessed data.

Number of PEx and CF-related hospitalizations through Week 24:

The analysis period for these variables will be the same as the PEx analysis period.

PEx will be summarized as described below:

- Number of events:
 - Number of PEx
 - Number of PEx requiring hospitalizations
 - Number of PEx requiring IV antibiotic therapy
 - Number of PEx requiring hospitalization or IV antibiotic therapy
- Duration of events:
 - Number of days with PEx
 - Number of days with PEx requiring hospitalizations
 - Number of days with PEx requiring IV antibiotic therapy
 - Number of days with PEx requiring hospitalization or IV antibiotic therapy

CF-related hospitalizations will be summarized as described below:

- Number of events:
 - Number of planned hospitalizations for CF (i.e., antibiotic therapy)
 - Number of unplanned hospitalizations for reasons other than antibiotic therapy for sinopulmonary signs/symptoms
- Duration of events:
 - Number of days of planned hospitalizations for CF (i.e., antibiotic therapy)
 - Number of days of unplanned hospitalizations for reasons other than antibiotic therapy for sinopulmonary signs/symptoms

For number of events variables, subjects with multiple defined events during the PEx analysis period will be counted multiple times. The annualized duration of events for each subject will be the total number of days with the defined events times 48 weeks divided by the total number of weeks on study up to the end of the PEx analysis period.

Absolute change in LCI_{2.5} from baseline through Week 24:

Analysis of this variable will be based on an MMRM similar to the analysis of the absolute change in ppFEV₁ from baseline through Week 24 with the baseline LCI_{2.5} included as a covariate instead of baseline ppFEV₁. Data obtained from Day 15, Week 4, Week 12, and Week 24 Visits will be included in the model. However, Day 15 Visit will not be included in the estimation of the average treatment effect through Week 24 as the treatment effect is not expected to reach the steady state at Day 15.

[figure not shown]
To better assess the longitudinal profile of the efficacy and pharmacodynamics assessments with repeated measures up to Week 24, the LS mean (SE) of the change from baseline at each post-baseline visit along with the 95% CI will be estimated from the corresponding MMRM. The LS mean (SE) at each visit will also be plotted. In addition, the post-baseline raw values and the absolute

[figure not shown]

change from baseline at each post-baseline visit will be summarized descriptively (n, mean, SD, median, minimum, and maximum).

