#### **12.3.3.2 Analysis of Secondary Efficacy and Pharmacodynamic Endpoints**

##### **Part B**

A summary of observed values and change from baseline will be provided for all secondary efficacy endpoints based on the FAS in Part B.

- **Absolute change in ppFEV1 from baseline through Week 24**

Absolute change from baseline in ppFEV1 will be analyzed using a mixed-effects model for repeated measures (MMRM) approach based on the FAS population. The MMRM will be used to estimate the within-group mean absolute change in ppFEV1 through Week 24. The model will include absolute change from baseline in ppFEV1 as the dependent variable, visit (as a class variable) as the fixed effect, with baseline ppFEV1 value and genotype group (F/F versus F/MF) as covariates. Data obtained from Day 15, Week 4, Week 8, Week 12, Week 16, and Week 24 Visits will be included in the model. An unstructured covariance structure will be used to model the within-subject errors.

The primary results obtained from the model will be the average treatment effect through Week 24. Note that the Day 15 Visit will not be included in the estimation of the average treatment effect through Week 24. The estimated mean change from baseline in ppFEV1 through Week 24, along with the corresponding 95% CI and 2-sided *P* value will be provided. The treatment effect at each post-baseline visit, obtained from the model, will be provided as well.

Summary statistics for change from baseline in ppFEV1 through Week 24 and at each visit will also be provided.

- **Absolute change in SwCl from baseline through Week 24**

Analysis of this endpoint will be based on an MMRM model that is similar to the analysis of absolute change from baseline in ppFEV1 through Week 24 with the baseline sweat chloride value included as a covariate instead of baseline ppFEV1. Data obtained from Day 15, Week 4, Week 12, and Week 24 Visits will be included in the model. However, the Day 15 Visit will not be included in the estimation of the average treatment effect through Week 24.

- **Absolute change in CFQ-R respiratory domain score from baseline through Week 24**

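### The model-based 95% CIs for the single-arm mean change leave out the sampling variance of the mean baseline, so they are too narrow for a population mean change wherever change depends on baseline

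*SAP*

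**What the plan says.** Part B is open-label and non-randomised, with no comparator (Protocol 9.2; SAP 7.3). For ppFEV1, Protocol 12.3.3.2 and SAP 9.3.2.2.2 agree on the target: "The MMRM will be used to estimate the within-group mean absolute change in" ppFEV1 through Week 24. Change from baseline is the response and visit is a fixed effect; the SAP adds the baseline "value and genotype group (F/F vs. F/MF) as covariates. The model will be estimated using restricted maximum likelihood". It continues "An unstructured covariance structure will be used to model the within-subject errors", with compound symmetry as the fallback if the model does not converge. Denominator degrees of freedom for the test "of fixed effects will be estimated using the Kenward-Roger approximation".

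The reported result is an average over Weeks 4, 8, 12, 16 and 24, with a two-sided 95% CI and a P value: "Note that the Day 15 Visit will not be included in the estimation of the average treatment effect through Week 24". Sweat chloride uses the same model "with the baseline sweat chloride included as a covariate instead of baseline" ppFEV1, and the CFQ-R respiratory domain, BMI, weight, height, their z-scores and LCI2.5 follow suit. LS means by visit, "along with the 95% CI will be estimated from the corresponding MMRM", are also reported and plotted.

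The SAP does not say at which baseline value, or with which genotype weights, the LS means are taken. It does not say whether the target is the mean change for the enrolled children's baselines or for the population they represent. SAP 9.3.2.2.3 calls sensitivity analysis not applicable.

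**The concern.** When two arms are compared, both adjusted means are taken at the same baseline value, so uncertainty about that value drops out of the difference. With one arm there is no difference to take. With complete data, the LS mean at the sample mean baseline and the observed genotype proportions is simply the raw mean change, so adjusting for baseline does not make it more precise. The model SE nevertheless removes the variance that baseline explains, because it treats the mean baseline as a known constant. Kenward-Roger corrects for estimating the covariance parameters. It does not correct for having sampled the baselines.

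At stake are the CIs and P values of the Part B MMRM endpoints. These will be read as statements about children aged 6 through 11, the population named in Protocol 5.2. The shortfall grows with the strength of the relation between change and baseline.

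**Working it through.** **The plan's own figure.** The only Part B sample-size figures are the probabilities of seeing at least one AE (SAP 7.2), and they reproduce:

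- N = 45: 1 − 0.95^45 = 90.06% and 1 − 0.90^45 = 99.13% (stated 90.0%, 99.1%).
- N = 50: 92.31% and 99.48% (stated 92.3%, 99.5%).

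No SE, CI width or power is stated for any efficacy endpoint, so there is no planned precision to compare with.

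**Inputs.** From the documents: n = 45 completers, a genotype target of about 25 F/MF and 20 F/F, the model above, and 95% two-sided intervals. Assumed: the correlation r between change and baseline, taken over |r| = 0 to 0.7, and LS means at the sample mean baseline, which is the usual default.

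**Formulae.** Let SD be the standard deviation of the reported change (one visit, or the average), b the baseline slope and s_x² the baseline variance.

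- SE from the model: SD × √(1 − r²)/√n.
- SE for the population mean change: SD/√n.
- Ratio of the two: √(1 − r²).
- Missing term: b² s_x²/n, where b = r × SD/s_x.
- Coverage: P(|T| ≤ t × ratio) with 42 df (45 − 3), where t is the 97.5% point.

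**Worked example.** The scale is assumed: SD of change 9, baseline SD 15, r = −0.5. Then b = −0.5 × 9/15 = −0.3. Model variance = 81 × 0.75/45 = 1.35. Missing term = 0.09 × 225/45 = 0.45. The sum is 1.80 = 81/45, so the SE should be 1.34, against 1.16 from the model.

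**Results at n = 45.** The last two columns are a simulation of the five-visit average, where r refers to that average: 25:20 genotype split, six visits, unstructured covariance, complete data, 4,000 replicates.

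| \|r\| | SE ratio | Coverage, formula | Coverage, simulated | After adding b²s_x²/n |
|---|---|---|---|---|
| 0 | 1.000 | 95.0% | 94.8% | 95.0% |
| 0.2 | 0.980 | 94.5% | 94.8% | 95.6% |
| 0.3 | 0.954 | 93.9% | 93.4% | 94.7% |
| 0.5 | 0.866 | 91.2% | 91.4% | 95.2% |
| 0.7 | 0.714 | 84.3% | 84.1% | 95.5% |

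At |r| = 0.5 the simulated model SE was 1.16, the corrected SE 1.35 and the empirical SE 1.36. For the narrower target, the mean change at the enrolled sample's mean baseline, the uncorrected interval covered 94.7% to 95.4% at every r.

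**In terms of pre-post correlation ρ.** With equal SDs before and after, r = −√((1 − ρ)/2), so the ratio is √((1 + ρ)/2): 0.997 at ρ = 0.99, 0.975 at 0.9, 0.922 at 0.7 and 0.866 at 0.5. Unequal SDs move it either way. With post-baseline SD 1.2 times baseline and ρ = 0.7, the ratio is √(0.7344/0.76) = 0.98. With 0.8 times and ρ = 0.5, it is √(0.48/0.84) = 0.76.

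**The through-Week-24 average.** Averaging removes visit noise and can strengthen the correlation with baseline. With equal SDs, ρ = 0.5 and an assumed between-visit correlation of 0.7, the average has variance (1 + 4 × 0.7)/5 = 0.76 relative to one visit. The ratio is then √[(0.76 − 0.25)/(0.76 + 1 − 1)] = 0.82, against 0.87 at a single visit.

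**Limits.** The simulation used complete data and n − 3 df in place of Kenward-Roger.

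**The case against.** The strongest reply is that inference conditional on the covariates is ordinary regression practice, and that the SAP never claims anything else. For that target the planned interval is right, and this stands. But the SAP does not state that target either. It calls the result an average treatment effect and attaches a P value, in a study meant to inform use in an age group. If the conditional target is intended, the text should say so and give the reference values.

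The size is not known: no document gives a correlation, so every figure above is a range over assumptions. This also stands. The consequences are limited too. Efficacy is secondary, P values are nominal (SAP 9.3.2), and the raw n, mean and SD of change are tabulated by visit, so a reader can form an unadjusted SE. Protocol 12.3.3.2 adds a through-Week-24 summary for ppFEV1, but neither document specifies one for the other averaged endpoints. Nominal status answers multiplicity. It does not answer a 95% interval that covers less than 95%.

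Two stronger readings are tempting, and the documents do not support them:

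- A reader might infer that every efficacy CI is too narrow. The shortfall is zero when change is unrelated to baseline and about 2% of the SE at |r| = 0.2. Six of the MMRM variables are growth measures, and for height and weight a very high pre-post correlation is likely. The exacerbation, hospitalisation and hedonic-scale summaries have no model CI.
- A reader might infer that the model loses many children for want of a baseline, because SAP 9.1 bars screening spirometry, sweat chloride and LCI values in children who took Orkambi or Symdeko in the 28 days before screening. All three are scheduled again on Day 1 (Protocol Table 3-4), so a child is lost only if the Day 1 value is also missing or invalid.

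**Conclusion.** The point holds in a limited form. As CIs for the mean change in the population, the planned intervals omit b²s_x²/n and are too narrow for each MMRM endpoint whose baseline slope is not zero. At n = 45 the shortfall is negligible up to about |r| = 0.2 and becomes material from about 0.4 to 0.5. Coverage is about 91% at 0.5 and 84% at 0.7. This rests on LS means taken at the sample mean baseline and on assumed correlations, so the size cannot be fixed for any particular endpoint. The complete-data point estimates, the descriptive primary safety analysis and the AE-based sample size do not change. The target left unstated is as much the defect as the SE, and it is worth correcting before the Part B data lock.

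**What to change.** In SAP 9.3.2.2.2, keep the planned MMRM and add three statements:

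1. The target is the mean change in the population represented by the FAS.
2. LS means are taken at the FAS mean baseline and at the observed genotype proportions. Equal genotype weights would not reproduce the raw mean under a 25:20 split.
3. For each visit and for the through-Week-24 average, (estimated baseline slope)² × (baseline variance)/n is added to the variance of the LS mean before the CI and P value are formed, n being the number of children in the model. This matches the single slope across visits in the planned model.

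Putting baseline into the response vector and reporting visit-minus-baseline contrasts is an acceptable alternative only under two conditions. Genotype must be retained, and the compound-symmetry fallback must not be applied across baseline and post-baseline values, because it would force baseline-to-post and post-to-post correlations to be equal. For ppFEV1 it also enlarges the unstructured matrix from 6 × 6 (21 parameters) to 7 × 7 (28).

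The cost is SAP wording and a small program change, with no new data. The right intervals are wider by 1/ratio − 1: about 5% at |r| = 0.3, 15% at 0.5 and 40% at 0.7. Where the slope is near zero they barely move (simulated SE 1.34 before and 1.36 after at r = 0).

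### Compound symmetry is the only fallback covariance; if it is used and the variance of change rises with time, the Week 24 growth intervals would be too narrow.

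*SAP*

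**What the plan says.** SAP 9.3.2.2.2 sets out the model for ppFEV1 in full: "The model will be estimated using restricted maximum likelihood", with Kenward-Roger degrees of freedom. On the covariance it says "An unstructured covariance structure will be used to model the within-subject errors", and then "If the model estimation does not converge, a compound symmetry covariance structure will be used instead". It names no other structure and no robust standard error. Protocol 12.3.3.2 names only the unstructured form.

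The growth endpoints refer back to that model: "Analysis of these variables will be based on an MMRM similar to the analysis of the absolute change" in ppFEV1, with the baseline covariate exchanged. Each is defined at one visit, for example "Absolute change in weight and weight-for-age z-score from baseline at Week 24". For these endpoints the SAP states "Data obtained from Day 15, Week 4, Week 8, Week 12, Week 16, and Week 24 Visits will be included in the model". The fallback is not restated for them, but nothing replaces it, so it carries over.

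The end of the same section adds, for all repeated-measures endpoints, a least-squares mean, standard error and 95% interval at each post-baseline visit, together with descriptive SDs by visit. SAP 9.3.2 calls the P values nominal. SAP 9.3.2.2.3 plans no sensitivity analysis.

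**The concern.** Compound symmetry assumes the same variance of change at Day 15 as at Week 24. For an average over visits this costs little, because high and low variances largely offset each other. For a single visit nothing offsets. Children who grow at different rates can be expected to drift apart in change from baseline, so variance at Week 24 may well exceed variance at Day 15. The pooled estimate then understates the Week 24 standard error, and the interval and P value at that visit are anti-conservative. Kenward-Roger adjusts for the small sample within the assumed structure; it does not repair the structure.

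Once the fallback is triggered it has to be followed, because choosing a better one after seeing the data would be post hoc. No other model-based analysis is planned that would check the result.

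**Working it through.** **Stated figure.** The documents give no figure for the precision of these models. The only numerical design figure for Part B is the chance of seeing at least one AE. It reproduces (1 − 0.95^45 = 0.9006, stated as 90.0%) but has no bearing here.

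**Inputs from the documents.** Six visits at t = 2, 4, 8, 12, 16 and 24 weeks; REML; two-sided 95% intervals; about 56 enrolled and 45 completing (SAP 7.2). The unstructured model has 6 × 7 / 2 = 21 covariance parameters.

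**Assumed.** The shape of the variance v(t) of change, because neither document gives one. Two rising shapes are used: v proportional to t (random walk) and v proportional to t² (random slope). In each, a share c of the Week 24 variance is held constant over time. That share stands for measurement error, baseline error and ordinary fluctuation.

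**Formula.** With complete data the compound-symmetry fit uses the mean of the visit variances at every visit, so

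width ratio at Week 24 = √(mean v / v at Week 24) = √(c + (1 − c)·m)

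- Linear: m = (66/6)/24 = 11/24 = 0.4583.
- Quadratic: m = (1060/6)/576 = 0.3067.

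For example, with c = 0.2 and the linear shape, √(0.2 + 0.8 × 0.4583) = √0.5667 = 0.753, which is 24.7% too narrow. Approximate coverage is 2Φ(1.96 × ratio) − 1.

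| Constant share c | Linear: too narrow (coverage) | Quadratic: too narrow (coverage) |
|---|---|---|
| 0 | 32.3% (81.5%) | 44.6% (72.2%) |
| 0.2 | 24.7% (86.0%) | 33.3% (80.9%) |
| 0.5 | 14.6% (90.6%) | 19.2% (88.7%) |
| 0.8 | 5.6% (93.6%) | 7.2% (93.1%) |
| 1 (flat) | 0% (95.0%) | 0% (95.0%) |

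**Check by simulation.** The compound-symmetry model with visit, baseline and genotype was fitted by REML with n = 56 and 300 runs per case. With complete data, the mean model standard error over the true one was:

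- c = 0: 0.673 (linear) and 0.553 (quadratic)
- c = 0.2: 0.751 and 0.668
- c = 0.5: 0.855 and 0.808

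These agree with the formula. With 20% random dropout and c = 0.2, the model standard error over the empirical SD was 0.69 and 0.63, with coverage of about 83% and 81%. At 300 runs these last figures are rough.

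**Comparison.** For the average over Weeks 4 to 24, with c from 0 to 0.5, the width ratio runs from 0.867 to 0.959. That is about 4-13% too narrow.

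**The case against.** The strongest reply is that the size is unknown. A reader might infer that variance does rise with time and that the Week 24 intervals would be 25-45% too narrow. The documents do not support that: they contain no SD, variance or correlation by visit for any growth endpoint. A shortfall of 25% or more needs √(c + (1 − c)·m) ≤ 0.75. That means c ≤ (0.5625 − 0.4583)/0.5417 = 0.19 for the linear shape, or c ≤ (0.5625 − 0.3067)/0.6933 = 0.37 for the quadratic. The 45% end needs a pure random slope with no error at all.

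The six growth outcomes also need not share one pattern. Z-scores are already adjusted for age and sex, and their age input is cut to whole months plus a half (SAP Appendix A). The COVID-19 addendum lets caregivers measure weight and height at home. Baseline error enters every change score. Each of these could add a constant component and shrink the effect. This objection stands.

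A reader might also infer that the unstructured fit is likely to fail for growth data. Neither the documents nor any calculation here shows that. The SAP does foresee non-convergence, since it provides a fallback, but how likely it is remains open.

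Finally, the endpoints are secondary in an open-label, single-arm study whose Part B primary endpoint is safety. No decision rule uses these intervals, and the descriptive SDs by visit would let a careful reader see unequal variances. That limits the weight of the point. It does not change the mechanism or its direction.

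**Conclusion.** The point holds as a conditional one. Two things must happen: the unstructured model fails to converge, and the variance of change rises over the visits. The model-based Week 24 interval for height, weight, BMI and their z-scores is then too narrow, by an amount set by the constant share in the table above: nothing if variance is flat, at most about 45%. The by-visit intervals for the other repeated-measures endpoints face the same mechanism; no size is claimed for them. This is a worthwhile but optional improvement to nominal secondary analyses and does not touch the primary safety evaluation.

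**What to change.** Replace the single fallback sentence in SAP 9.3.2.2.2 with an ordered list and use the first structure that converges:

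1. heterogeneous Toeplitz (11 parameters at six visits)
2. heterogeneous AR(1) (7)
3. heterogeneous compound symmetry (7)
4. plain compound symmetry (2) with an empirical (sandwich) standard error

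The first three estimate the Week 24 variance from Week 24 data, so the complete-data width ratio returns to about 1.00. The fourth ensures that the analysis is always defined. Because Kenward-Roger is built on the model-based standard error, the SAP should also state which degrees of freedom go with step 4. The list should be said to apply to every endpoint that borrows the ppFEV1 model.

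The cost is about one sentence in the SAP and a few more parameters to estimate when a fallback is needed. Nothing changes when the unstructured model converges.
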